4.3.3 Safety Analysis

Safety analysis will be based on the entire study population.

Any adverse events occurring within 7 days after vaccination, serious adverse events, or deaths will be summarized as n (%) of participants having experienced the AE(s), and SAEs or death by arms. Comparisons will be done between full-dose and fractional-dose arms with the control arm, using a Fisher's exact test.

All AEs will be coded to a "Preferred Term" (PT) and primary associated "System-Organ Class" (SOC) according to the MedDRA dictionary (Medical Dictionary for Regulatory Activities, version 25.0).

Counts and proportions will be provided overall and for each PT within each SOC. AE(s) will be tabulated overall and by grade, and by type of AEs:

- AEs non SAEs occurring with 7 days after vaccination
- SAEs
- SAEs leading to death

5. Statistical Tables to be Generated

<Consider appropriate tables for each of these categories and some examples are provided>

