7.2.1 Summary of vaccine safety

The most frequently reported adverse reactions include fever, irritability, injection site reactions including pain, erythema, swelling or induration, decreased appetite, drowsiness and diarrhoea. Serious reactions are rare.

Extending the use of the 5-dose multi-dose vial to provide 25 administrations may increase the risk of injection site reactions e.g. swelling and localised inflammation due to contamination. The preservative contained in the vial should minimise this risk.

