Safety analysis will be based on the entire study population. Safety and tolerability of PCV10 will be assessed by comparing the frequency (%) of AEs and SAEs in full-dose and fractional-dose arms to the control arm using the Fisher's exact test. Safety data will be presented in tabular and/or graphical

format and summarized descriptively. Data will be analyzed according to an intention-to-treat approach. In the unlikely event of clusters receiving incorrect interventions, or being only partially vaccinated, per-protocol analyses will be repeated on the primary endpoint.

13 Quality assurance and control

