3.1.3 Randomization and Blinding

Following the results of the baseline survey, clusters will be randomized in a 3:3:1 ratio, with 27 clusters randomized to receive a campaign with the full dose, 27 clusters randomized to receive a campaign with the fractional dose and 9 clusters randomized to the control arm. Randomization will be stratified by proximity to nearest health center (<5 km vs ≥5 km). In the event of significant imbalance in carriage of VT pneumococci between clusters in the baseline survey, randomization will also be stratified by baseline prevalence, after a decision by the trial steering committee. An equal or proportional number of clusters will be randomized to each study arm from each stratum. The study statistician randomization will prepare the material to generate the list (blocked randomization with fixed block size if only one stratum, by minimisation if more than one stratum), and the final list will be generated by an independent statistician who has no contact with study participants. Study implementation will be blinded to the extent possible. Vaccination nurses will not be blinded to the vaccine they are giving, but they will not communicate vaccine allocation to other members of the team or to participating villages. Villages randomized to the control arm will not receive any “dummy” intervention, so will not be blinded to their group allocation. The trial will be observer-blind in that personnel at KWTRP will be blinded to group allocation until after the completion of culture and serotyping in each survey.

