Data on Adverse Events (AEs) will be collected in a passive surveillance system for 7 days following vaccination (focusing on AEs at the injection site) and data on Serious Adverse Events (SAEs) for 28 days following vaccination. A health professional from the study team will be based in the nearest health centre to the vaccinated villages for 28 days after the vaccination activities and will be the key notifiers of AEs and SAEs to the study team. Moreover, the community health workers from the vaccinated villages will be asked to act as a focal point and communicate to the study team any events that occur during the follow-up period. During the vaccination activities, caretakers will be informed about vaccine safety and will be asked to contact the community health worker or to attend the nearest health centre in case of a health problem.

Data concerning SAEs from participants in villages allocated to the control group will be collected between the first vaccination date up to 28 days after the last vaccination date performed in villages that were allocated to full or fractional dose and located in the catchment area of the same health facility.

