3.2.2 Safety Assessments

The safety outcomes are AE(s) at the injection site occurring within 7 days after vaccination and SAE(s) occurring within 28 days after the vaccination. SAEs from participants in clusters allocated to the control group will be collected during a period of time from the first vaccination date up to 28 days after the last vaccination date performed in clusters allocated to full or fractional dose, in the geographical area sharing the same health center.

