3.2.2.2 Adverse Events

An adverse event (AE) is defined as any untoward medical occurrence in a clinical trial subject to whom a vaccine has been administered; it does not necessarily have a causal relationship with the vaccine/vaccination. In this study, the recording AEs will be limited to injection-site reactions as site pain injection, redness, swelling, itchiness, infection, etc.

In addition to the diagnostic, the intensity, the start and end dates, the outcome, the causality assessment with the vaccine, the seriousness criterion and the actions taken. Age and sex of the participant experiencing the AE(s) will also be collected.

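### Injection-site reactions in each vaccine arm are tested against an uninjected control arm, and no fractional-versus-full safety contrast is named

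*Combined protocol and SAP*

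**What the plan says.** **Named comparison.** SAP 4.3.3 summarises AEs, SAEs and deaths as n (%) by arm, then says "Comparisons will be done between full-dose and fractional-dose arms with the control arm", with Fisher's exact test. Protocol section 12 (Data Analysis) is explicit that both event types are meant: "comparing the frequency (%) of AEs and SAEs in full-dose and fractional-dose arms to the control arm using the Fisher's exact test".

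**What counts as an AE.** SAP 3.2.2: "The safety outcomes are AE(s) at the injection site occurring within 7 days after vaccination". SAP 3.2.2.2: "In this study, the recording AEs will be limited to injection-site reactions". Protocol section 8 has the same restriction. Protocol 6.1, under vaccine safety, is broader: it speaks of recording all AEs and SAEs up to 28 days.

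**Control arm.** SAP 3.1.3: "Villages randomized to the control arm will not receive any" dummy intervention. SAP 3.1.4 and 3.2.2 define a control collection window for SAEs only.

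**Dose-specific concern.** Protocol 7.2.1: "Extending the use of the 5-dose multi-dose vial to provide 25 administrations may increase the risk of injection site reactions".

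**SAE follow-up.** Vaccinees are followed for 28 days. Control SAEs are collected "between the first vaccination date up to 28 days after the last vaccination date performed in villages" in the same health-facility catchment (SAP 3.1.4). In the same section, "the community health workers from the vaccinated villages will be asked to act as a focal point"; no equivalent is described for control villages.

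**Denominators.** SAP 3.1.5 uses children actually vaccinated in the vaccine arms and target-age children from the census in control. SAP 4.3.3 refers to the entire study population.

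**The concern.** A local reaction to an injection cannot occur in a child who was not injected, so the planned AE test can only confirm that injections cause injection-site reactions. Both vaccine arms will probably differ significantly from control whatever the dose. A reader who sees two small p-values learns nothing about whether repeated puncture of the vial makes local reactions more frequent in the fractional arm. That is the local-safety question the protocol itself raises, and the safety objective concerns events after fractional and full doses.

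The SAE comparison with control is legitimate in principle, but children observed for different lengths of time are compared as simple percentages. A longer control window would by itself raise the control percentage.

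**Working it through.** **Inputs from the documents.** 27, 27 and 9 clusters; about 600 target-age children per cluster; two-sided 0.05 level.

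**The plan's own figure.** 54 × 600 = 32,400 targeted children, as stated. Per vaccine arm: 27 × 600 = 16,200. Taking the same cluster size for control: 9 × 600 = 5,400.

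**Assumptions.** Campaign coverage of 60%, 80% or 100%, giving 9,720, 12,960 or 16,200 vaccinees per arm. AE and SAE risks, L and between-cluster variation are not in the documents and are also assumed, over the ranges shown.

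**AE test against a structural zero.** Smallest count reaching p < 0.05 (Fisher, two-sided) against 0/5,400:

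| Vaccinees | Smallest significant count | p | p with one event fewer |
|---|---|---|---|
| 9,720 | 9 | 0.031 | 0.057 |
| 12,960 | 10 | 0.040 | 0.066 |
| 16,200 | 12 | 0.046 | 0.076 |

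At 12,960 vaccinees the threshold is 10/12,960 = 0.077%. The probability of at least 10 reactions is 83% if the true risk is 0.1% and above 99.9% if it is 0.2%.

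**What the test misses.** Suppose 26/12,960 (0.20%) react after the full dose and 52/12,960 (0.40%) after the fractional dose. Against control, p = 0.00015 and p < 0.0001. The doubling between doses, which is not a named comparison, has a naive Fisher p of 0.004.

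**The alternative contrast.** With 480 vaccinees per cluster (600 × 0.8), 27 clusters per arm, AE risk r and between-cluster coefficient of variation (CV) k, the 95% half-width for fractional minus full is t(52 df) × √{2[r(1 − r)/480 + k²r²]/27}, with t = 2.007.

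| AE risk | Half-width, k = 0.3 to 0.5 | Width relative to the naive interval |
|---|---|---|
| 0.1% | 0.080 to 0.083 percentage points | 1.05 to 1.08 |
| 0.2% | 0.116 to 0.124 | 1.07 to 1.14 |
| 0.5% | 0.19 to 0.22 | 1.13 to 1.30 |

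With each arm's own risk in the formula, the example above gives a difference of 0.20 percentage points, with half-width 0.15 (k = 0.3) to 0.16 (k = 0.5).

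**SAE window.** Let L be the days from first to last vaccination in a catchment. Control follow-up is 28 + L days against 28. With a constant SAE rate and no vaccine effect, the expected vaccine-to-control risk ratio is 28/(28 + L): 1.00, 0.90, 0.80 and 0.67 for L = 0, 3, 7 and 14.

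**Offset from surveillance.** If control capture were 80% of that in vaccinated villages and L = 7, the control count would change by 0.8 × 35/28 = 1.0. The two effects would cancel.

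**The case against.** **Tables by arm already allow the dose comparison.** SAP 4.3 displays all results by group and gives a general chi-square or Fisher rule for safety, and the objective is only to assess occurrence. This is true, and a reader could derive the difference. But the section that names the contrasts names only comparisons with control, and SAP 1.1 says the SAP exists to prevent post hoc choices.

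**AEs might be broader than local reactions.** Protocol 6.1 can be read that way. Protocol section 8 and SAP 3.2.2 and 3.2.2.2 are more specific and probably govern, but 6.1 should be reconciled with them. Even on the broader reading, no control AE window exists.

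**Fractional versus full is not fully masked.** A reader might infer that villages do not know their dose. Protocol 7.11 says only that nurses will not communicate allocation, while protocol 9.9.1 has information sessions covering the assignment of villages to arms. With passive reporting, that could influence what is reported. The contrast is still the better one, because both arms receive an injection and are described as having the same surveillance.

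**The longer control window might be read as making the vaccine look protective.** The documents do not support a direction. L is not stated and may be zero, and protocol 7.6 and SAP 3.1.4 aim to vaccinate an area at the same time. Community focal points and caretaker briefing are described only for vaccinated villages, which could lower control ascertainment.

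**Individual-level safety tests might be read as inflating SAE error.** For rare SAEs this is not shown. Simulated Fisher error at L = 0 was 2.8% to 4.1% at SAE risks of 0.05% to 0.1% (CV 0.3 to 0.5), so this is not part of the point.

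**Conclusion.** The AE part holds on the text, with one reconciliation needed (protocol 6.1). The control count is zero by design, the test is uninformative, and the contrast that answers the protocol's own vial concern is not named. The thresholds of 9 to 12 events rest on about 600 children per cluster and assumed coverage; the logic does not depend on them.

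The SAE part is secondary and conditional. It applies only if L > 0, its size is 28/(28 + L) under a constant rate, and its net direction is unknown.

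A child-day analysis should not be read as making the SAE comparison sound. In simulation, a cluster-level t-test on child-day rates kept error at 3% to 5%, but only under equal ascertainment. Selection also remains: vaccinees attended and passed the screening in protocol 7.6.1, whereas control is every target-age child in the census.

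The carriage endpoint is unaffected. This should be changed, but it does not threaten the primary result.

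**What to change.** 1. In SAP 4.3.3 and protocol section 12, replace the AE comparison with control by a fractional-minus-full risk difference and 95% CI among vaccinees, allowing for clustering (27 against 27 clusters; for example, cluster-level risks with a t interval). Note that reporting is passive. Reconcile protocol 9.9.1 with protocol 7.11 and SAP 3.1.3 on whether villages know their dose arm, and protocol 6.1 with section 8 on which AEs are recorded.
2. Compare SAEs with control as rates per child-day (vaccinees × 28; target-age census children × window length), or over a matched 28-day window, by a cluster-level method because there are only 9 control clusters. State the window for a control cluster whose catchment has no vaccinated cluster. List as limitations the unequal village-level surveillance and the comparison of screened vaccinees with all target-age census children; this change removes only the window-length bias.
3. As wording only, align the entire study population in SAP 4.3.3 with the safety groups in SAP 3.1.5.

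**Cost.** Mostly text, using vaccinee counts, census counts and vaccination dates. Village is not among the AE and SAE items listed in SAP 3.2.2.1 and 3.2.2.2, so confirm that the forms identify it. AE intervals widen modestly, as shown above. Child-day rates assume a roughly constant SAE rate over the window. The change departs from the protocol's stated method and must be explained, as SAP 1.1 requires.

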5.1 Demographic and Baseline

Table 1.1 Summary of Screening
Table 1.2 Summary of Participant Disposition by intervention group, Analysis Population - Randomized Cluster
Table 1.4 Summary of Protocol Deviations by intervention group - ITT Population
Table 1.5 Summary of Demographics and Baseline Characteristics by intervention group, participants and Cluster level - ITT Population

5.2 Primary and Secondary Analyses

5.3 Safety Analysis

Adverse Events

Table 3.1 Summary of adverse events (AEs) by intervention group
Table 3.2 Adverse events (AEs) by MedDRA coding (SOC and PT) by intervention group, Safety population
Table 3.3 Severity of adverse events (AEs) , Safety population
Table 3.6 Relatedness of adverse events (AEs) , Safety population
Table 3.7 Outcome of adverse events (AEs) , Safety population

Serious Adverse Events

Table 3.1 Summary of serious adverse events (SAEs) by intervention group
Table 3.2 Serious Adverse events (SAEs) by MedDRA coding (SOC and PT) by intervention group, Safety population
Table 3.6 Relatedness of serious adverse events (SAEs), Safety population
Table 3.7 Outcome of serious adverse events (SAEs), Safety population
Deaths
Table 3.22 Summary of deaths by study arm, Safety population

6. Statistical Listings to be Generated

<Adapt and amend as needed>

Participant Data Listings

Listing 1.1 Participants who are screen-failures
Listing 1.3 Listing of protocol deviations
Listing 1.5 Exclusion of villages/cluster from PP populations

Safety Listings

Listing 2.1 Listing of Serious adverse events (SAEs)
Listing 2.3 Listing of Adverse events (AEs)
Listing 2.5 Listing of death narratives

7. Statistical Graphs to be Generated

<Adapt and amend as needed>

Figure 1.1 Study flowchart of study arms, and analysis populations
